10.1.2 Evaluation of Best Overall Response

The best overall response is the best response observed until progression/recurrence and is determined as indicated in the table below:

Target Lesions	Non-Target Lesions	Evaluation of New Lesions	Best Overall Response
CR	CR	No	CR
CR	SD	No	PR
PR	Non-PD	No	PR
SD	Non-PD	No	SD
PD	Any	Yes or No	PD
Any	PD	Yes or No	PD
Any	Any	Yes	PD

10.2 Safety

Routine safety and tolerability will be evaluated from the results of reported signs and symptoms, scheduled physical examinations, vital sign measurements, and clinical laboratory test results. More frequent safety evaluations may be performed if clinically indicated or at the discretion of the investigator. All patients who receive at least one dose of any of the two agents are evaluable for safety.

Physical Examination

Complete and symptom-directed physical examinations will be performed by a licensed physician (or physician's assistant or nurse practitioner).

Vital Signs

Vital signs (blood pressure, respiratory rate, pulse rate and temperature) will be obtained.

Safety Laboratory Determinations

Laboratory evaluations will be performed as noted in the flow chart.

11 STATISTICAL CONSIDERATIONS

11.1 Primary objective

This is a non-randomized phase II trial designed to evaluate the combination of pembrolizumab plus cabozantinib. Prior clinical trials of first-line gemcitabine-carboplatin in cisplatin-ineligible patients have been performed. One study identified an objective response rate of 36%, with a median progression-free survival of only 4.8 months in 56 treated patients.²³ A second study of 60 patients noted an objective response rate of 38.4%, with a median progression-free survival of 7.6 months.²⁴ It has also been reported a 26% ORR in patient treated with pembrolizumab with locally advanced or metastatic urothelial cancer²⁵. ORR will be analyzed descriptively. The proportion of objective responses will be reported and a 95% one-sided exact binomial confidence interval (Clopper-Pearson) will be calculated for ORR. With 35 evaluable subjects the lower bound of the 95% confidence interval will extend no more than 26% from the observed proportion. If there are 17 or more objective responses in 35 patients the confidence interval will exclude 32%. Adding another 10% for unevaluable patients that may be enrolled, a total of up to 39 patients will be enrolled.

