Diagnosis and Main Eligibility Criteria	
Cisplatin-ineligible urothelial carcinoma
 
Key Inclusion Criteria:
 
• Histologically proven transitional cell or urothelial carcinoma (UC).• Metastatic (any N+ or M1) or locally advanced, unresectable (T4bN0) disease.• Measurable disease is required as determined by RECIST v1.1.• Cisplatin-ineligibility based on ≥ 1 of the following:
○ Estimated CrCl of between ≥ 40 and < 60 ml/min (CG formula)○ ECOG PS ≥ 2○ Hearing loss○ Baseline neuropathy○ Patient refusal 
Key Exclusion Criteria:
 
• Prior chemotherapy for metastatic/ advanced urothelial carcinoma.• Prior chemotherapy treatment for localized urothelial carcinoma that has been completed less than 6 months before registration.

	
• Small-cell or sarcomatoid component in histology.
Study Product, Dose, Route, Regimen	Pembrolizumab 200mg IV q 3 weeks with cabozantinib administered 40mg orally, with dose reductions to 20 mg daily. Subsequent dose reduction to 20 mg every other day to improve tolerability is allowed.
Duration of administration	Patients will receive therapy until treatment discontinuation criteria is met or until 12 months from start of therapy
Reference therapy	Study treatment will be compared to pembrolizumab as single agent.
Statistical Methodology	A 95% one-sided exact binomial confidence interval (Clopper-Pearson) will be calculated for ORR. With 35 evaluable subjects the lower bound of the 95% confidence interval will extend no more than 26% from the observed proportion. If there are 17 or more objective responses in 35 patients the confidence interval will exclude 32%. Secondary analyses will include an association of risk group (based on performance status and visceral metastasis) with PFS. Stratified Kaplan-Meier methodology will be used to associate risk group (based on performance status and visceral metastasis) with PFS.

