4.2 Number of Patients

A total of up to 39 subjects will be enrolled with the objective of having a minimum of 35 evaluable subjects for the primary objective.

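### The 26% precision figure for 35 evaluable patients is too loose: the stated exact one-sided bound is never more than 15.3 percentage points below the observed response rate

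*Combined protocol and SAP*

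**What the plan says.** Section 11.1 (Primary objective) says that ORR will be analysed descriptively and that "a 95% one-sided exact binomial confidence interval (Clopper-Pearson) will be calculated for ORR". It then describes what the sample size delivers: "With 35 evaluable subjects the lower bound of the 95% confidence interval will extend no more than 26% from the observed proportion". The Study Summary, under Statistical Methodology, repeats the figure: "the lower bound of the 95% confidence interval will extend no more than 26% from the observed proportion". Neither place derives the 26 or says whether it means percentage points or a fraction of the estimate.

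Two companion figures follow in Section 11.1. One is a threshold: "If there are 17 or more objective responses in 35 patients the confidence interval will exclude 32" (per cent). The other is the enrolment allowance: "Adding another 10% for unevaluable patients that may be enrolled, a total of up to 39 patients will be enrolled". Section 4.2 confirms 35 as the minimum number of evaluable subjects.

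**The concern.** The method, confidence level, sidedness and sample size are all stated, so the largest distance from estimate to lower bound is a fixed number that can be computed exactly. A distance of 26 points looks far too large for 35 patients.

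It also sits badly beside the threshold in the next sentence. At 17/35 the estimate is 48.6%. A lower bound 26 points below that would be 22.6%, which does not exclude 32%. For the threshold to hold, the gap at 17/35 must be under 48.6 − 32 = 16.6 points.

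Section 11.1 gives no power calculation. The precision sentence and the 17/35 threshold are therefore the only quantitative support for n = 35, and a reader who relies on the precision sentence gets a wrong picture of what 35 patients provide.

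**Working it through.** **Inputs, all from Section 11.1.** n = 35 evaluable; one-sided 95%, so α = 0.05 in the lower tail; Clopper-Pearson; stated ceiling 26; threshold 17/35 against 32%; 10% allowance for unevaluable patients.

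**Formula.** For x responses, the lower bound L(x) is the α quantile of a Beta(x, n − x + 1) distribution, with L(0) = 0. The distance is x/n − L(x), and its maximum is taken over x = 0, …, 35.

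**The plan's companion figures reproduce.**
- L(17) = 33.8%, above 32%, and L(16) = 31.2%, below 32%. So 17 is the smallest count that excludes 32%. The chance of 17 or more responses when the true ORR is 32% is 0.030.
- The two-sided 95% lower bound at 17/35 is 31.4%, which does not exclude 32%. The threshold therefore works only with the one-sided bound that the plan names.
- 35/0.90 = 38.9, rounded up to 39.

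**The precision figure does not reproduce.** With the stated method at n = 35:

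| Responses | Observed | Lower bound | Distance (points) |
|---|---|---|---|
| 9 | 25.7% | 14.1% | 11.6 |
| 17 | 48.6% | 33.8% | 14.8 |
| 22 | 62.9% | 47.6% | 15.3 (maximum) |
| 28 | 80.0% | 65.7% | 14.3 |

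As a check, the probability of 22 or more responses in 35 at p = L(22) is 0.0500. The unrounded maximum is 0.15298. The stated ceiling exceeds it by 26 − 15.3 = 10.7 points and is 26/15.3 = 1.7 times as large.

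**Other readings at n = 35.**

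| Reading | Maximum (points) |
|---|---|
| Wald or Wilson, one-sided 95% | 13.9 |
| Wald or Wilson, two-sided 95% | 16.6 |
| Exact, two-sided 95% | 17.9 |
| Wald, two-sided 95%, continuity-corrected | 18.0 |
| Exact, two-sided 98% | 21.0 |
| Exact, two-sided 99% | 23.1 |
| Full width, exact two-sided 90% | 29.8 |
| Full width, exact two-sided 95% | 34.6 |

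None gives 26.

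**Relative reading.** If 26% means a fraction of the estimate, the quantity is 1 − L(x)/(x/n). It is 45.1% at 9/35, 30.4% at 17/35 and 26.6% at 20/35, and first falls below 26% at 21/35 (25.5%). The sentence would then be false for every count from 1 to 20.

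**Sample size that a 26-point ceiling describes.** With the one-sided 95% exact bound, the maximum distance is 26.5 points at n = 13 and 25.4 at n = 14. With the two-sided 95% bound it is 26.6 at n = 17 and 25.7 at n = 18.

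**The case against.** The strongest reply is that the sentence is true. It gives an upper limit and does not claim that the limit is attained; in percentage points the limit holds for every outcome, one-sided or two-sided. Nothing else rests on it: the threshold, the 35 and the 39 do not use it, and the reported interval will be computed from the data. The looseness is conservative, so nobody is promised precision that the trial will not deliver, and the next sentence already tells a careful reader that the gap at 17/35 is under 16.6 points. The comparison with n = 14 also starts from a figure of unknown origin and could be misread as criticism of the sample size.

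Most of this stands, and it is why the point is minor. It does not make 26 the right number. A precision statement is there to show what the sample size provides, and a ceiling that 14 patients would meet does not do that for 35. The n = 14 comparison uses the plan's own one-sided method, which the threshold confirms; it says nothing against n = 35. The missing unit is a further defect, since the other natural reading makes the sentence false over much of the range.

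**Conclusion.** The concern holds and is minor. With 35 evaluable subjects and a one-sided 95% Clopper-Pearson interval, the lower bound is at most 15.3 percentage points below the observed ORR. The stated 26 is a valid limit in points, but it is 10.7 points too loose and is not the figure that this method and sample size give.

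The result rests only on inputs stated in Section 11.1, with the distance read in percentage points. It applies to exactly 35 evaluable subjects; with more, the maximum is smaller (14.4 points if all 39 were evaluable). The documents do not show where 26 came from. The 17/35 threshold, the sample size, the enrolment figure and the planned analysis are unaffected.

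**What to change.** In Section 11.1 and in the Statistical Methodology row of the Study Summary, replace the precision sentence with wording such as:

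> For 35 evaluable subjects, the distance from the observed ORR down to its one-sided 95% Clopper-Pearson lower bound is at most 15.3 percentage points.

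This corrects the number, names the bound and states the unit. Leave the 17/35 threshold, the 35 evaluable subjects and the total of 39 as they are. The cost is one sentence in two places, with no change to sample size, threshold or analysis.

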11.2 Secondary Objectives and Endpoints

The secondary objectives are to evaluate progression free survival at 6 months and overall survival of pembrolizumab + cabozantinib in subjects with UC. Kaplan-Meier methods and associated confidence intervals will be used to analyze PFS and OS. Subjects will be evaluated for survival for 6 months or until death after discontinuation of study treatment. The proportion of subjects who exhibit an objective response will be reported along with an exact binomial confidence interval. As an additional secondary analysis, stratified Kaplan-Meier methodology will be used to associate risk group (based on performance status and visceral metastasis) with PFS.

11.3 Exploratory Objectives and Endpoints

We are planning to evaluate molecular markers of tissue in tissues to correlate with response to drug treatment and blood markers to evaluate pharmacodynamic markers of drug mechanisms. However, the specific biomarker tests and assays have not yet been finalized. Once a decision has been made, a statistical plan will be written and an amendment to the protocol will be made.

12 REGISTRATION GUIDELINES

Patients must meet all of the eligibility requirements listed in Section 5 prior to registration.

Study related screening procedures can only begin once the patient has signed a consent form. Patients must not begin protocol treatment prior to registration.

Treatment should start within five working days after registration.

To register eligible patients on study, complete a Clinical Trials Office Patient Registration Form and submit to: [contact].

13 DATA SUBMISSION SCHEDULE

The Case Report Forms (CRFs) are a set of (electronic or paper) forms for each patient that provides a record of the data generated according to the protocol. CRF's should be created prior to the study being initiated and updated (if applicable) when amendments to the protocol are IRB approved. **Data capture should be restricted to endpoints and relevant patient information required for planned manuscripts.** These forms will be completed on an on-going basis during the study. The medical records will be source of verification of the data. During the study, the CRFs will be monitored for completeness, accuracy, legibility and attention to detail by a member of the Research Compliance Office. The CRFs will be completed by the Investigator or a member of the study team as listed on the Delegation of Duties Log. The data will be reviewed no less than annually by the Data and Safety Monitoring Committee. The Investigator will allow the Data and Safety Monitoring Committee or Research Compliance Office personnel access to the patient source documents, clinical supplies dispensing and storage area, and study documentation for the above-mentioned purpose. The Investigator further agrees to assist the site visitors in their activities.

14 SPECIAL INSTRUCTIONS

14.1 Correlative Studies

Correlative studies may include but are not limited to analysis that identify the mechanisms of response and resistance to immunotherapy, at the cellular and molecular levels.

14.1.1 Collection of Tumor Tissue

Participants who opt in to the optional tissue collection, tissue may be collected at pre-screening from an urothelial carcinoma diagnostic procedure (soft tissue biopsy or TURBT) or during screening from a soft tissue biopsy (only for patients who do not sign the pre-screening ICF). Subjects are also offered the option of a fresh soft-tissue biopsy or TURBT again prior to treatment at cycle 4 or after. Up to ten sections will be collected during the TURBT and up to six cores will be obtained at the time of soft tissue biopsy. These tissues will be used to establish a biomarker panel predictive of treatment efficacy which will be validated in future clinical trials.

Testing may include, but is not limited to:

- Multiomics platforms
- Immunohistochemistry
- Flow cytometry
- Ex vivo treatment to predict treatment efficacy

Instructions for processing and analysis will be detailed in the lab manual.

14.1.2 Collection of Blood for Correlative Analysis

Participants who opt in to the optional blood collection, up to 36mL of blood may be collected on C1D1, C2D1, C4D1, C7D1, C13D1, and at end of treatment.

These samples will be used to test for biomarkers of disease response and prediction of treatment effect. Testing may include, but is not limited to:

- C-reactive protein (CRP)
- Neutrophil to Lymphocyte ratio
- Hemoglobin
- Cytokine/chemokine/interferon assays
- Flow cytometry
- Mass cytometry
- T-cell kinetics
- Genome analysis

Specimen collection and processing instructions can be found in the lab manual.

14.1.3 Collection of Stool Samples for Correlative Analysis

Collection of stool samples and administration of Stool Questionnaire may occur prior to treatment on cycles 1, 2, 4, 7, 13, and at the end of treatment. Stool collection kits will be given to subjects at the clinic visit preceding the collection time point and they will be instructed to collect the sample within 3 days prior to the time points noted above and answer the questionnaire provided in the stool kit (Appendix B).

These samples will be used to determine a predictive microbiome signature associated with therapeutic response.

Testing may include, but is not limited to:

- 16S ribosomal RNA sequencing
- Cultivation of microbes
- Shotgun metagenomics

Specimen collection and storage instructions can be found in the lab manual and the patient stool collection instructions.

15 ETHICAL AND REGULATORY CONSIDERATIONS

15.1 Informed consent

Informed consent will be obtained from all research participants prior to performing any study procedures using the most recent IRB approved version.

15.2 Institutional Review

Before study initiation, the investigator must have written and dated approval/favorable opinion from the IRB/IEC for the protocol, consent form, subject recruitment materials (e.g., advertisements), and any other applicable patient-facing documents. The investigator should also provide the IRB/IEC with a copy of the Investigator Brochure or product labeling information.

The investigator or designee should provide the IRB/IEC with reports, updates and other information (e.g., expedited safety reports, amendments, and administrative letters) according to regulatory requirements or institution procedures.

15.3 Data and Safety Monitoring Plan

A Data and Safety Monitoring Committee (DSMC) is established at Huntsman Cancer Institute (HCI) to ensure the well-being of patients enrolled on Investigator Initiated Trials that do not have an outside monitoring review. The roles and responsibilities of the DSMC are set forth in the NCI-approved Data and Safety Monitoring (DSM) plan. The activities of the committee include reviewing adverse events (including SAEs), deviations, important medical events, significant revisions or amendments to the protocol, and approving cohort/dose escalations. If the DSMC and/or the PI have concerns about unexpected safety issues, the study will be stopped and will not be resumed until the issues are resolved. The DSMC also reviews and approves audit reports generated by the Research Compliance Office.

This is a Phase II, multicenter, study classified as high risk per the NCI-approved DSM plan.

Each high risk study may be assigned a physician member of the DSMC as medical monitor, or in rare cases, an external medical monitor. The medical monitor will be notified of all serious adverse events (SAEs). Approval of the medical monitor is required for all dose escalations. SAEs occurring in patients treated at HCI or its affiliates will also be reviewed by the full DSMC monthly. The full committee will also review all toxicities for patients on treatment and within 30 days of their last treatment on a quarterly basis.

Each high-risk study will be assigned a dedicated research compliance officer who will monitor the trial. High-risk trials will be monitored by RCO personnel after the first patient is enrolled and every three months thereafter during active enrollment. The RCO monitor will review the study status and summarize enrollment, toxicities, SAEs, dose escalation, statistical endpoints (e.g., stopping rules), deviations, etc. for the full DSMC membership at the regularly scheduled meetings. Amendments that

increase risk, change dosing, or impact study objectives will be reviewed by the DSMC and approved by the PRMC and IRB. High-risk trials will be formally reviewed by the DSMC after the first patient is enrolled and then quarterly thereafter.

An initial audit of high-risk studies will be conducted by the RCO approximately one year after enrollment begins and annually thereafter. Audits of high-risk studies may be conducted more frequently as requested by the DSMC, IRB, PRMC, RCO management, or the PI.

A safety analysis will be performed after the first 6 patients enroll and receive treatment. During this stage, the decision to continue enrollment will be made by the Data Safety and monitoring committee (DSMC). When all 6 subjects in the have been followed for at least 21 days following first dose of pembrolizumab and cabozantinib, all available safety data will be considered in a decision to continue enrollment.

15.4 Adverse Events / Serious Adverse Events

This study will utilize the CTCAE (NCI Common Terminology Criteria for Adverse Events) Version 5.0 for AE and SAE reporting.

15.4.1 Adverse Events (AE)

An adverse event is the appearance or worsening of any undesirable sign, symptom, or medical condition occurring after starting the study drug even if the event is not considered to be related to study drug. For the purposes of this study, the terms toxicity and adverse event are used interchangeably. Medical conditions/diseases present before starting study drug are only considered adverse events if they worsen after starting study drug. Abnormal laboratory values or test results constitute adverse events only if they induce clinical signs or symptoms, are considered clinically significant, or require therapy.

The collection of adverse events will begin after the signature of the consent form and end 30 days post the last dose of study treatment.

Information about all adverse events, whether volunteered by the subject, discovered by investigator questioning, or detected through physical examination, laboratory test or other means, will be collected and recorded and followed as appropriate.

Adverse events should be evaluated to determine:

1. The severity grade based on CTCAE v.5.0 (grade 1-5)
2. Its relationship to the study drug(s) (definite, probable, possible, unlikely, not related).
3. Its duration (start and end dates or if continuing at final exam)
4. Action taken (no action taken; study drug dosage adjusted/temporarily interrupted; study drug permanently discontinued due to this adverse event; concomitant medication taken; non-drug therapy given; hospitalization/prolonged hospitalization)
5. Whether it constitutes an SAE

All adverse events will be treated appropriately. Such treatment may include changes in study drug treatment as listed in the dose modification section of this protocol (see section 7 for guidance). Once an adverse event is detected, it should be followed until its resolution, and assessment should be made at each visit (or more frequently, if necessary) of any changes in severity, the suspected relationship to the study drug, the interventions required to treat it, and the outcome.

Information about common side effects already known about the investigational drugs is described in the Drug Information (section 3) and (the most recent Investigator Brochures). This information will be included in the patient informed consent and will be discussed with the patient during the study as needed.

All adverse events will be immediately recorded in the patient research chart.

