7.1 Dose Modifications and Guidelines for Adverse Event Management for Cabozantinib

Subjects will be monitored for AEs from the start of treatment through 30 days after the date of the last dose of cabozantinib treatment. Subjects will be instructed to notify their physician immediately at the onset of any AE. Causality assessment of AEs will be determined by the investigator. AE severity will be graded by the investigator in accordance with CTCAE v.5.0. The following should be taken into consideration in decisions regarding dose modifications (reductions or interruption):

- As a general approach, all AEs should be managed with supportive care at the earliest signs of toxicity considered related to the study treatment. Should this be ineffective, dose interruptions and/or reductions should be considered to prevent worsening of toxicity.
- The assigned starting dose for cabozantinib is 40 mg/day. Dose reductions are permitted per PI discretion (see Table 7.1). Dose re-escalation level (See 7.2) of cabozantinib is permitted.
- Dose interruptions and/or reductions should be implemented for unacceptable toxicity. Doses may be modified at any time while on study.
- Interruption of cabozantinib treatment for AEs may occur at any time per investigator discretion. If treatment is interrupted due to AEs for more than 6 weeks, all study treatment should be discontinued unless there is unequivocal evidence that the subject is benefitting. In this situation, a subject may be able to restart therapy with a dose reduction upon resolution of the toxicity.

- Dose interruptions for reason(s) other than related AEs (e.g., surgical procedures) can be longer than 6 weeks per the discretion of the investigator.

Table 7.1

Assigned dose	Dose Level Reduction
40-mg cabozantinib oral, qd	20-mg cabozantinib oral, qd.
20-mg cabozantinib oral, qd	20-mg cabozantinib oral, qad

Table 7.2

Assigned dose	Dose Level Escalation
20-mg cabozantinib, oral qad	20-mg cabozantinib, oral qd
20-mg cabozantinib, oral qd	40-mg cabozantinib, oral qd

Table 7.3: Dose Modifications of Cabozantinib for Treatment-Related AEs

CTCAE v.5.0 Grade	Recommended Guidelines for Management ^a
Grade 1 AEs	Add supportive care as indicated. Continue cabozantinib treatment at the current dose level if AE is manageable and tolerable.
Grade 2 AEs that are tolerable and are easily managed	Continue cabozantinib treatment at the current dose level with supportive care.

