7.2 Dose modification and toxicity management guidelines for pembrolizumab

Dose modification and toxicity management for immune-related AEs associated with Pembrolizumab

AEs associated with pembrolizumab exposure may represent an immunologic etiology. These immune-related AEs (irAEs) may occur shortly after the first dose or several months after the last dose of pembrolizumab treatment and may affect more than one body system simultaneously. Therefore, early recognition and initiation of treatment is critical to reduce complications. Based on existing clinical trial data, most irAEs were reversible and could be managed with interruptions of pembrolizumab, administration of corticosteroids and/or other supportive care. For suspected irAEs, ensure adequate evaluation to confirm etiology or exclude other causes. Additional procedures or tests such as bronchoscopy, endoscopy, skin biopsy may be included as part of the evaluation. Based on the severity of irAEs, withhold or permanently discontinue pembrolizumab and administer corticosteroids. Dose modification and toxicity management guidelines for irAEs associated with pembrolizumab are provided in Table 7.9.

Table 7.9: Dose modification and toxicity management guidelines for immune-related AEs associated with Pembrolizumab.

General instructions:				
Immune-related AEs	Toxicity grade or conditions (CTCAE v.5.0)	Action taken to pembrolizumab	irAE management with corticosteroid and/or other therapies	Monitor and follow-up
Pneumonitis	Grade 2	Withhold	
Administer corticosteroids (initial dose of 1-2mg/kg prednisone or equivalent) followed by taper	
Monitor subjects for signs and symptoms of pneumonitisEvaluate subjects with suspected pneumonitis with radiographic imaging and initiate corticosteroid treatmentAdd prophylactic antibiotics for opportunistic infections
	Grade 3 or 4, or recurrent grade 2	Permanently discontinue		

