- PT/INR, aPTT if patients are on active anticoagulant therapy and require monitoring
- B-type Natriuretic peptide
- Urinalysis including urine protein creatinine ratio

Optional Blood and Stool Collection and administration of Stool Questionnaire for correlatives see section 14

Adverse event collection for 30 days

CT scans of the chest/abdomen/pelvis and response assessment by RECIST v1.1 to be performed at the end of treatment visit only if patient has come off for reasons other than progression

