9.5 Follow-up Assessments

Patients will be followed for 6 months after cessation of study treatment for survival.

Patients removed from therapy without evidence of progression will undergo radiological examination every 12 weeks or earlier, if clinically warranted.

Patients will be followed for SAEs for 90 days after the cessation of treatment

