15.4.2 Serious Adverse Event (SAE)

Information about all serious adverse events will be collected and recorded. A serious adverse event is an undesirable sign, symptom or medical condition which:

- Is fatal or life-threatening
- Results in persistent or significant disability/incapacity
- Is medically significant, i.e., defined as an event that jeopardizes the patient or may require medical or surgical intervention to prevent one of the outcomes listed above
- Causes congenital anomaly or birth defect
- Requires inpatient hospitalization or prolongation of existing hospitalization, unless hospitalization is for:
 - Routine treatment or monitoring of the studied indication, not associated with any deterioration in condition (procedures such as central line placements, paracentesis, pain control)
 - Elective or pre-planned treatment for a pre-existing condition that is unrelated to the indication under study and has not worsened since the start of study drug
 - Treatment on an emergency outpatient basis for an event not fulfilling any of the definitions of a SAE given above and not resulting in hospital admission
 - Social reasons and respite care in the absence of any deterioration in the patient's general condition

Serious adverse event collection will begin after the signature of the consent form and end 90 days after the last dose of study treatment or until new cancer treatment is initiated, if sooner.

Any death from any cause while a patient is receiving treatment on this protocol or up to 30 days after the last dose of protocol treatment, or any death which occurs more than 30 days after protocol treatment has ended but which is felt to be treatment related, must be reported.

Toxicities which fall within the definitions listed above must be reported as an SAE regardless if they are felt to be treatment related or not. Toxicities unrelated to treatment that do NOT fall within the definitions above, must simply be documented as AEs in the patient research chart.

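### New non-serious immune-related adverse events starting more than 30 days after the last dose need not be collected, so the toxicity table can only understate late immune toxicity

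*Combined protocol and SAP*

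**What the plan says.** **All adverse events.** Section 15.4.1 sets collection to "end 30 days post the last dose of study treatment". Section 9.4, on the end-of-treatment assessments, lists "Adverse event collection for 30 days". Section 7.1 uses the same length but counts it from one drug: monitoring runs "through 30 days after the date of the last dose of cabozantinib treatment". In section 15.3 the monitoring committee is to "review all toxicities for patients on treatment and within 30 days of their last treatment" each quarter.

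**Serious adverse events.** Section 9.5 reads: "Patients will be followed for SAEs for 90 days after the cessation of treatment". Section 15.4.2 has SAE collection "end 90 days after the last dose of study treatment or until new cancer treatment is initiated, if sooner". It counts medically significant events as serious. It also requires reporting of a death more than 30 days after treatment if it is thought to be treatment-related.

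**Expected timing of immune toxicity.** Section 7.2 says that irAEs "may occur shortly after the first dose or several months after the last dose of pembrolizumab treatment".

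**Endpoint and later contact.** Objective 1.2.3 is a tabulation of adverse events by drug attribution. The end-of-treatment visit falls 28 ± 14 days after treatment (9.4 and study calendar). After it come survival follow-up to 6 months by telephone or record review, and scans every 12 weeks for patients who stopped without progression. No laboratory tests are scheduled in that period.

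**The concern.** The protocol gives a risk period for immune toxicity that runs to several months off drug, but it requires the non-serious part to be collected for only one month. Several irAEs in Table 7.9 can be found and managed without admission and may not be serious, for example thyroid dysfunction, Grade 2 liver enzyme elevation or a creatinine rise.

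Toxicity of the combination is a stated secondary objective. An event that is not collected cannot appear in its table, so any error lies in one direction. The committee's quarterly review of all toxicities stops at the same 30 days and has the same gap.

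**Working it through.** The plan states no figure on this point, so there is none to reproduce. The check compares the windows, and an illustration of size follows.

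**1. What is collected, by days since the last dose of study treatment**

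| Days | New non-serious AE | New SAE |
|---|---|---|
| 0–30 | yes (15.4.1, 9.4) | yes |
| 31–90 | not required | yes, unless new cancer treatment has started (15.4.2) |
| 91 to about 183 | not required | no, apart from treatment-related deaths |

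Taking 6 months as 182.6 days, the part of follow-up without collection of new non-serious events is 182.6 − 30 = 152.6 days, and 152.6 / 182.6 = 84%. With a 90-day window it would be 182.6 − 90 = 92.6 days, or 51%.

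**2. Does another section close the gap?**

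- Section 6.2.5 provides additional follow-up after the end-of-study visit for related AEs that are still ongoing and for related SAEs that arise later. It does not mention new non-serious AEs.
- The instruction in 15.4.1 to follow an event to resolution applies to events already detected.
- The contact to 6 months is for survival.
- No section sets a longer period for irAEs or for events of special interest.

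**3. The end-of-treatment visit**

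The visit may take place from day 28 − 14 = 14 to day 28 + 14 = 42. Its laboratory panel (9.4) includes TSH, free T4 and T3, liver enzymes, bilirubin, creatinine and glucose, which are markers of several irAEs in Table 7.9. Suppose an abnormality is first found on days 31 to 42, is non-serious, and would otherwise count as an AE under 15.4.1 (symptomatic, clinically significant or needing therapy). Read literally, it lies outside the window although a scheduled test found it.

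**4. Illustration of size**

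Inputs: N = 39, the maximum enrolment (4.2), and an assumed proportion p with a first non-serious irAE after day 30. The documents give no value for p. Expected number missed = 39p; chance of missing at least one = 1 − (1 − p)^39.

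| Assumed p | Expected missed | Chance of missing at least one |
|---|---|---|
| 1% | 39 × 0.01 = 0.4 | 1 − 0.99^39 = 32% |
| 2% | 39 × 0.02 = 0.8 | 1 − 0.98^39 = 55% |
| 5% | 39 × 0.05 = 2.0 | 1 − 0.95^39 = 86% |
| 10% | 39 × 0.10 = 3.9 | 1 − 0.90^39 = 98% |

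All 39 patients are treated as at risk after day 30. Some will have died, withdrawn or been lost by then, so for a given p these figures are upper values.

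**The case against.** The 30-day AE and 90-day SAE windows are used consistently and look deliberate. The sentence in 7.2 is a warning to clinicians, not a collection rule, so the sections do not contradict each other. The longer SAE window is already a partial answer to late toxicity. Objective 1.2.3 is descriptive, with no threshold or comparator. Neither the primary response rate nor the safety decision on the first six patients, taken at 21 days after first dose, depends on late events. All of this stands, and it limits the weight of the point.

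A reader might infer that late immune toxicity is never recorded, or is reported as absent after day 30. The documents do not support that. SAEs are collected to day 90 whether related or not, and some Grade 3 hepatitis, colitis, new diabetes or hypophysitis could qualify as medically significant without admission. Detected events are followed to resolution. Under 15.4.1 the clock starts at the last dose of study treatment, so a patient who stops pembrolizumab and stays on cabozantinib, as 7.2 allows, remains under full collection.

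A reader might also infer that a question at existing contacts would recover the missing events at no real cost. That is not supported either. No day-90 contact is scheduled, record review may involve no contact with the patient, and irAEs that show only in blood tests will not surface without tests.

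None of this supplies a rule for collecting new, late, non-serious irAEs.

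**Conclusion.** The point holds in a limited form. Non-serious irAEs that first arise more than 30 days after the last dose of study treatment are not required to be collected, although the protocol itself says irAEs can arise months after pembrolizumab. The tabulation for objective 1.2.3 can therefore understate late irAEs but cannot overstate them through this route.

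The direction is certain; the size is not. It depends wholly on an unknown late-onset rate: from about 0.4 patients at 1% to 3.9 at 10%, assuming all 39 remain at risk. It would be tempting to conclude that several patients will be missed, but the documents give no rate that would support that. The 12-month treatment limit in 6.9 does not create the problem, since anyone who stops treatment and remains in follow-up is in the same position.

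This is an inexpensive improvement to safety reporting. It is not a flaw in the primary analysis.

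**What to change.** Amend 15.4.1, 9.4, 9.5 and the review sentence in 15.3 together:

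- Keep 30 days for general AEs, but extend collection at least through the end-of-treatment visit, so that findings at that visit on days 31 to 42 count.
- Record any new immune-related AE, serious or not, that comes to light during the SAE follow-up already required to 90 days after the last dose, or in the survival telephone or record review.
- Tabulate irAEs by onset: to day 30, days 31 to 90, and later. Flag onset after new anticancer therapy rather than dropping the event.
- State that ascertainment after the end-of-treatment visit is passive. No laboratory tests are scheduled then, and the only visits are scans for patients who stopped without progression, so late asymptomatic events may still be missed.
- Reconcile 7.1, which counts the window from the last cabozantinib dose, with 15.4.1, which counts it from the last dose of study treatment.

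These changes concern data collection and reporting only. The cost is slightly more data collection and one further table. Reported irAE rates may be somewhat higher, and attribution of some late events will be uncertain, especially after new therapy.
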